## 6.6 Analysis of Primary Safety Endpoint

The primary safety endpoint is defined as the incidence of neurological death or major ipsilateral stroke (National Institute of Health Stroke Scale [NIHSS] increase of  $\geq 4$  for  $>24$  hours) at any time during the follow-up period (12 months  $\pm$  8 weeks). Total number and frequency of subjects with neurological death or major ipsilateral stroke will be presented with two-sided 95% confidence intervals of the rate.

The primary safety endpoint will be met if the upper bound of the confidence interval is  $\leq 15\%$ . Table 6-3 below summarizes the clinical outcomes of the three studies from the background that specifically address endovascular treatment of wide-necked basilar and MCA aneurysms. Information about these studies is summarized in Section 5, “Background for Proposed Trial”. A complication rate was identified for each article by including events which could indicate stroke (i.e., thromboembolic events, ischemic events, artery dissection, hemorrhage, aneurysm rupture, and cranial nerve palsy). The overall weighted average of the incidence rate derived from the meta-analysis of these three trials was 13%. This provides the basis for selecting 15% for the primary safety endpoint of the Barrel study.

**Table 6-3 Safety Rates Reported in the Literature**

Study	Number of Patients in the Trial	Number of Aneurysms in the Trial	Number of Events	Complication* Rate
Fargen 2013	45	45	6	13.3%
Spiotta 2011	19	19	4	21.1%
Zhang 2014	23	23	1	4.3%
Total / Weighted Average	87	87	11	12.6%

\* Complications include events that could indicate stroke (i.e., thromboembolic events, ischemic events, artery dissection, hemorrhage, aneurysm rupture and cranial nerve palsy)

Note: These articles were reviewed closely to ensure that if the information was available, that patients with multiple complications were counted only once, as well as to ensure that asymptomatic events and events resolving within 24 hours were excluded.

## 6.7 Analysis of Secondary Endpoints

Secondary endpoints will be analyzed with descriptive statistics along with a 95% confidence interval. Descriptive statistics for categorical variables will include the number and percentage of subjects in each category, with two-sided 95% confidence intervals of the percentage of subjects in each category. Descriptive statistics of continuous variables will include sample size, mean, standard deviation, minimum, maximum, and 95% confidence interval of the mean.

## 6.8 Analysis of Baseline Demographics and Procedural Characteristics

All clinically relevant baseline variables will be tabulated using descriptive statistics.

## 6.9 Pre-planned Subgroup Analyses

Subgroup analysis of demographic factors of age group ( $\leq 65$  and  $> 65$ ) and gender (male and female) will be

performed.

## 6.10 Handling of Missing Data

Multiple imputation technique will be implemented to assess the impact of missing data on the analysis of efficacy endpoint. For the parameters summarized based on the incidence, an imputed dataset where the binary outcome for subjects who withdraw prior to the scheduled assessment will be derived using the Markov Chain Monte Carlo (MCMC) algorithm specifying missing at random (MAR). The subject characteristics and demographic factors to be included in the multiple imputation procedure to generate the imputed datasets for analysis will be defined in the Statistical Analysis Plan (SAP).

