## 6.2 Primary Analysis

The goal of the primary analysis will be to demonstrate that the Barrel® VRD device performs better than the combined historical control treatments for complete occlusion rate at 12 months. The hypothesis to be tested is:

$$H_0: \pi_B = \text{HC} \text{ versus } H_A: \pi_B > \text{HC}$$

Where  $\pi_B$  is the proportion of successful outcomes for the Barrel® VRD device and HC is the combined overall historical control success rate. Success is defined as a subject with a Raymond Grade of 1 (100% occlusion) at 12 months  $\pm$  8 weeks in the absence of retreatment, parent artery stenosis (> 50%), or target aneurysm rupture. This hypothesis will be tested using an exact one sample binomial test at ( $\alpha = 0.025$ ). Exact 95% confidence intervals will be constructed.

The meta-analysis analysis mentioned above provides an overall estimate for historical control success rate of 42.48% with a 95% confidence interval of (31.90%, 53.06%).

Although the meta-analysis provides the basis for deriving a historical control success rate, it does not allow exact comparison due to the author-evaluated Raymond Grades used in the studies versus the proposed core laboratory grade reporting. Moreover, the reported rates in the published literature do not take into account patients lost to follow-up in their final calculation of occlusion rates. Conversely, the Barrel study employs a more stringent intent-to-treat (ITT) methodology that treats those patients lost to follow up as treatment failures. A review of the literature shows that onsite angiographic evaluators report 20 to 60% higher Raymond Grade success rates than those reported by core laboratories. Rezek et al. (2013) states “Core laboratories tend to report higher rates of unfavorable outcomes compared with self-reporting centers. Indeed, the rate of unfavorable outcomes was 43.6% greater in core laboratories compared with noncore laboratory studies.” McDougall CG et al. (2014) states, “in 36% of cases, the local investigators reported a better degree of occlusion than did the core laboratory.”

Unfortunately only one paper, Rezek et al. (2014), provided sufficient detail of the operator and core laboratory

results, in a population that is representative of the patient population that is proposed in the protocol, to allow statistical analysis of the difference.

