### 6.3 Sample Size Calculation

In actuality, the real objective of this study is to demonstrate that the Barrel® VRD is comparable to historical controls. Therefore the historical success rate of 28% was selected as the historical control value. The Barrel® VRD will be considered successful if its lower 95% confidence limit is greater than 28%.

Table 6-2 presents the sample size necessary to have an 80% power with a significance level of 2.5% for rejecting the null hypothesis in favor of the alternative when the true success rate for the Barrel® VRD is as specified. The hypotheses to be tested are:

$$H_0: \pi_B = 28\% \text{ versus } H_A: \pi_B > 28\%$$

Where  $\pi_B$  is the proportion of successful outcomes for the Barrel® VRD device.

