**Table 6-2 Sample Size**

	True Success Rate for Barrel ® VRD Device							
% Raymond Grade 1	38%	39%	40%	41%	42%	43%	44%	45%
Sample Size	177	145	123	107	92	80	71	62

Principal [name] and the clinical team agree that there is potentially an advantage to the Barrel® VRD device and thus a 41% success rate is the expected performance. Assuming a 10% dropout rate, the number of subjects required to be treated for the study is 119. The total number of subjects enrolled will be 159 to account for up to 25% of subjects who consent for the trial and withdraw prior to treatment or are determined to be ineligible.

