**Table 12-1 Schedule of Tests**

Tests and Evaluations	Screening/ Baseline	Procedural (Day 0)	30 days ±14 days	180 days ±30 days	12 months ±8 weeks	Unscheduled Visit
Inclusion/Exclusion	X					
Demographics	X					
Medical history	X					
Medications	X	X	X	X	X	X
Blood Labs	X					
Modified Rankin Score	X		X	X	X	
NIHSS Score	X			X	X	X 
Adverse Events		X	X	X	X	X
Angiography 	X 	X		X 	X	
Raymond Grade Scale	X 	X		X	X	

MRA is acceptable if performed according to the standard of practice at the participating institution.

The baseline angiogram must be taken no more than 180 calendar days prior to the procedure.

For previously coiled aneurysms

If an angiogram is performed as standard patient care it should be sent to the core laboratory for analysis.

If visit is related to target aneurysm or potentially associated adverse event

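### The planned check on missing 12-month outcomes shares nearly the same assumption as the primary analysis, so it cannot show whether success depends on missing patients doing worse

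*Protocol*

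**What the plan says.** - **Primary analysis.** Section 6.5 defines the ITT set as eligible, consented subjects with attempted delivery of the device. It bases the primary efficacy and safety analyses on observed data. The per-protocol set requires a completed 12-month angiographic evaluation.
- **Check on missing data.** Section 6.10: "Multiple imputation technique will be implemented to assess the impact of missing data on the analysis of efficacy endpoint". The binary outcome of subjects who withdraw before the assessment "will be derived using the Markov Chain Monte Carlo (MCMC) algorithm specifying missing at random (MAR"). Only the patient-level covariates of the imputation model are left to the SAP.
- **Conflicting text.** Section 6.2 says the study's ITT approach counts patients lost to follow-up as failures.
- **Subjects without an implant.** Sections 12.6.5, 12.6.7 and 12.6.8.2 take subjects with attempted but unsuccessful implantation out of the study after the 30-day visit.
- **Success rule.** Section 6.2: "This hypothesis will be tested using an exact one sample binomial test at" a level of 0.025. Section 6.3: the device "will be considered successful if its lower 95% confidence limit is greater than 28" per cent. Section 8.1.1 still gives 23% as the bound.
- **Size.** "thus a 41% success rate is the expected performance", and "Assuming a 10% dropout rate, the number of subjects required to be treated for the study is 119" (Section 6.3, with Table 6-2).

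**The concern.** A sensitivity analysis is informative when it changes the assumption that the main analysis cannot verify. Here that assumption is that patients without a 12-month grade would have done about as well as those with one. Missing-at-random imputation keeps this, apart from differences that the covariates explain. There is no control arm, so no comparison exists in which such a bias could partly cancel. The per-protocol set drops the same patients and is no check either.

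The assumption is least plausible for subjects in whom implantation failed. They belong to the ITT set, and they have no 12-month grade because the device was not placed. Section 6.10 speaks only of subjects who withdraw, so their handling is unclear. If they are imputed, they receive roughly the success rate of implanted patients. If they are left out as unobserved, a failure of the device drops out of the efficacy rate.

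At stake is whether a result just above the goal can be relied on.

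**Working it through.** **Inputs.** Goal 28%, one-sided 0.025, 80% power (Section 6.3: "80% power with a significance level of 2.5% for rejecting the null hypothesis"); exact binomial test (Section 6.2); true rate 41%, 10% dropout, 119 treated (Section 6.3); 107 evaluable (Section 6). Expected missing: 119 − 107 = 12.

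**1. The plan's own figures.** With n = 107, the smallest count with P(X ≥ r | 0.28) ≤ 0.025 is r = 40. The exact level is 0.0221 and power at 41% is 0.804. No smaller n reaches 80%, so 107 reproduces, as do the other seven sizes in Table 6-2. 107/0.9 = 118.9, giving 119.

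**2. Imputation against observed cases.** Take an intercept-only missing-at-random model, p = 40/107 and Rubin's rules:
- within-imputation variance W = p(1−p)/119
- between-imputation variance B = p(1−p)(1/12 + 1/107)(12/119)²
- W + B = p(1−p)[1/119 + 12/(107×119)] = p(1−p)/107

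That is the observed-case variance. The estimate is 37.4% either way, and the approximate lower limit is 0.3738 − 1.96 × 0.0468 = 28.2% either way. A simulation with 20,000 imputations agrees (standard error 4.67 against 4.68 points).

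Covariates can move the answer. Assume a factor present in 30% of patients, with 20% missing there and 10% missing overall, so (0.10 − 0.06)/0.70 = 5.7% missing in the rest. If success rates differ by 20 points (47% and 27%, overall 41%), the observed-case rate is (0.66×0.47 + 0.24×0.27)/0.90 = 41.7%, a shift of 0.7 points. For differences of 5 and 10 points the shift is 0.2 and 0.3.

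**3. What the missing outcomes can do.** Exact lower limits against 28%:

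| Observed successes | Of 107 | Of 119, all missing fail | Missing successes needed |
|---|---|---|---|
| 40 | 28.2% | 25.2% | 4 of 12 |
| 41 | 29.1% | 26.0% | 3 |
| 42 | 30.0% | 26.8% | 2 |
| 43 | 30.8% | 27.5% | 1 |
| 44 | 31.7% | 28.3% | 0 |

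On 119 the test needs 44 successes.

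**4. How likely that is.** At a true 41% among the observed, P(40 ≤ X ≤ 43) = 0.804 − 0.527 = 0.278. The chance of reversal is the sum over x = 40 to 43 of P(X = x) × P(Y < 44 − x), where Y is binomial with 12 missing patients and success rate q:

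| q among missing | Chance of reversal |
|---|---|
| 0% | 28% |
| 20% | 11% |
| 30% | 5% |
| 41% | 2% |

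**5. False success at the extreme.** If the true rate over all 119 is 28% and the 12 missing all fail, the observed-case rate is 0.28 × 119/107 = 31.1%, and P(X ≥ 40) = 10.0% against a nominal 2.5%.

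**The case against.** **The current method has a stated reason.** Section 4.1 calls missing-equals-failure an extreme form of imputation, unsuitable for the primary analysis, and says FDA recommended multiple imputation. That supports the primary analysis and the imputation. It does not argue against a tipping-point table as a sensitivity analysis. Nor is the failure end of such a table foreign to this trial: the 42.5% in Table 6-1, from which the goal is derived, is 37/87, with the 87 − 63 = 24 patients without imaging in the denominator.

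**The SAP may add such an analysis.** It may. But the protocol fixes the method for this purpose and defers only the covariates.

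**The extreme overstates the risk.** This stands. The 28% needs all 12 missing patients to fail. The design expectation is 0.41 × 107 = 43.9 successes, and at 44 the result survives even that.

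**The goal is not settled.** This also stands. Against the 23% in Section 8.1.1, 40/119 with a lower limit of 25.2% would pass, and the reversals shown above would not occur.

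A reader might also infer more than the protocol supports:
- *That the imputation draws from a normal model and rounds to yes or no.* Section 6.10 names neither. If it did round at 0.5, the distortion over all 119 would be only about 0.2 to 0.3 points.
- *That core-lab grades at 180 days were wrongly left out as predictors.* Section 6.10 lists no predictors, and choosing them is ordinary SAP content. The 180-day imaging is also conditional (Table 12-1: "If an angiogram is performed as standard patient care it should be sent to the core laboratory for analysis").
- *That no worst-case rule appears anywhere.* Section 6.2 contains one. The defect is that it conflicts with Sections 6.5 and 6.10.

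**Conclusion.** The point holds. The one operative method for judging the impact of missing efficacy outcomes cannot answer that question, because it shares the observed-case assumption almost entirely: the answers are identical without covariates and differ by at most 0.7 points in the range tried. A passing result of 40 to 43 out of 107 would depend on the missing patients, needing between 4 and 1 successes among the 12. The probability of landing there is 28% at a true 41%, and the chance of an actual reversal runs from 28% (all missing fail) through 11% and 5% to 2% (missing succeed at 20%, 30% and 41%).

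These figures assume 12 of 119 missing, 41% among the observed, independent outcomes and the 28% goal. The number of failed implantations is not given, so their share of the 12 is unknown.

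It would be too strong to say that missing data are likely to decide the trial, or that the observed-case primary analysis is itself wrong. Two contradictions need reconciling in any case: Section 6.2 against Sections 6.5 and 6.10 on lost patients, and Section 6.3 against Section 8.1.1 on the bound.

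**What to change.** 1. Keep the observed-case primary analysis and the multiple imputation.
2. State that subjects with a known failure (such as retreatment, target aneurysm rupture or no device implanted) count as failures and are not imputed, even without a 12-month grade.
3. Pre-specify a tipping-point table on all attempted-delivery subjects. Let the number of successes among those still missing run from none (missing equals failure) to all (missing equals success), and test each entry exactly against the reconciled goal.
4. Remove or correct the statement in Section 6.2 that lost patients are treated as failures, and give one bound in Sections 6.3 and 8.1.1.

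The cost is protocol and SAP text and one added table, with no extra patients or visits. The downside is that a result near the threshold may be shown to be fragile. Counting failed implantations as failures will also lower the observed rate by an amount that the protocol's figures do not allow to be estimated.

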## 7. Objectives

The purpose of this study is to evaluate the safety and efficacy of the Reverse Medical Barrel® VRD for Adjunctive Treatment to Embolic Coils for Wide-neck, Intracranial, Bifurcating/Branching Aneurysms of Middle Cerebral and Basilar Arteries.

## 8. Overall Trial Design

The BARREL Study is a prospective multi-center single-arm study of the Barrel® VRD. Up to 159 subjects will be enrolled at up to 28 centers to ensure 119 subjects are treated. After obtaining informed consent, screening and baseline assessments, and eligibility confirmation, qualifying patients will receive the study treatment.

### 8.1 Primary Outcome Measures

#### 8.1.1 Primary Endpoints

- Primary Efficacy Endpoint: The number of Barrel® VRD treated aneurysms achieving Raymond Grade I (100% occlusion) at 12 months  $\pm$  8 weeks in the absence of retreatment, parent artery stenosis ( $> 50\%$ ), or target aneurysm rupture. The primary efficacy endpoint will be met if the lower bound of the 95% confidence interval is  $> 23\%$ .
- Primary Safety Endpoint: Incidence of neurological death or major ipsilateral stroke (National Institutes of Health Stroke Scale [NIHSS] increase of  $\geq 4$  for  $>24$  hours) at any time during the follow-up period (12 months  $\pm$  8 weeks). The primary safety endpoint will be met if the upper bound of the confidence interval is  $\leq 15\%$ .

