An analysis of this data provided an adjustment of 36% between the operator results and the core laboratory results. This difference was consistent with the other published results. After adjustment, the estimated historical success rate for core lab results is 28%. The corresponding adjusted confidence interval is (23%, 33%).

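### Section 8.1.1 sets the efficacy pass mark at a lower 95% limit above 23%, but Section 6.3 and the sample size rest on 28%

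*Protocol*

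**What the plan says.** Section 8.1.1 defines the primary efficacy endpoint and attaches a decision rule: "The primary efficacy endpoint will be met if the lower bound of the 95% confidence interval is" above 23%.

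Section 6.3 gives a different rule for the same endpoint. It states that "the historical success rate of 28% was selected as the historical control value", writes the null hypothesis as a success proportion of 28%, and says the device "will be considered successful if its lower 95% confidence limit is greater than 28"%. Table 6-2 then gives sample sizes for 80% power at a 2.5% significance level. The row for a 41% true rate gives 107, which becomes 119 treated after a 10% dropout allowance.

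Section 6.2 names the method: "This hypothesis will be tested using an exact one sample binomial test at" a level of 0.025, and "Exact 95% confidence intervals will be constructed". Its hypothesis is written against a symbol for the historical control rate, not a number. It also reports the core-lab-adjusted historical estimate of 28% with an interval of 23% to 33%, so 23% appears there as the lower end of that interval. Only Section 6.3 fixes the test value.

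**The concern.** The trial has one formal hypothesis test, in a single arm, against a fixed number. The pass mark is therefore the whole decision rule, and the protocol gives two of them five percentage points apart. Neither section says which governs. A reader looking for the endpoint rule would naturally go to Section 8.1.1 and find the lower one.

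Two things are at stake. A band of plausible results would be a success under one section and a failure under the other. And if the 23% rule were applied, the chance of declaring success at the stated null rate of 28% would be far above the stated 2.5%.

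**Working it through.** **Inputs.** Thresholds 23% (Section 8.1.1) and 28% (Section 6.3); exact one-sample binomial test at one-sided 0.025 and exact 95% interval (Section 6.2); 80% power and expected rate 41% (Section 6.3); 107 evaluable and 119 treated (Sections 6 and 6.3); primary analysis on observed data (Section 6.5).

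**Step 1: reproduce the plan's own figure.** For each n, take the smallest r with P(X ≥ r | n, 0.28) ≤ 0.025, then find the first n with P(X ≥ r | n, p) ≥ 0.80.

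- At p = 0.41 this gives n = 107, r = 40, level 0.0221 and power 80.4%.
- The other seven entries also reproduce exactly: 177, 145, 123, 92, 80, 71 and 62 for 38%, 39%, 40%, 42%, 43%, 44% and 45%.
- A normal approximation would give 100 at 41%, so the table was built with the exact test.
- 107 / 0.90 = 118.9, rounded up to 119. 119 / 0.75 = 158.7, rounded up to 159.

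Against 23%, the power at n = 107 and a true rate of 41% would be 98.0%. The stated size and power therefore belong to 28%.

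**Step 2: what each rule requires.** The exact lower limit L for x successes solves P(X ≥ x | n, L) = 0.025.

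| Successes of 107 | Observed rate | Exact lower limit | Section 8.1.1 (> 23%) | Section 6.3 (> 28%) |
|---|---|---|---|---|
| 33 | 30.8% | 22.3% | fails | fails |
| 34 | 31.8% | 23.1% | meets | fails |
| 39 | 36.4% | 27.4% | meets | fails |
| 40 | 37.4% | 28.2% | meets | meets |

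The rules disagree for 34 to 39 successes inclusive. Wilson limits give the same band; Wald limits give 35 to 39.

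**Step 3: how often the rules disagree, n = 107.** The disagreement probability is P(X ≥ 34) − P(X ≥ 40).

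| True rate | P(pass, 23% rule) | P(pass, 28% rule) | Difference |
|---|---|---|---|
| 28% | 0.221 | 0.022 | 0.199 |
| 33% | 0.641 | 0.194 | 0.448 |
| 35% | 0.787 | 0.336 | 0.451 |
| 41% | 0.980 | 0.804 | 0.176 |

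**Step 4: dependence on the denominator.** If all 119 treated subjects are observed, the exact lower limits are 22.9% at 37, 23.7% at 38, 27.5% at 43 and 28.3% at 44. The disputed band is then 38 to 43. At a true rate of 28% the 23% rule passes with probability 19.6%, against 2.1% for the 28% rule. The counts shift with n, but the conflict remains.

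**The case against.** The strongest reply is that the intent is plain. The numerical hypothesis, the chosen control value, the success statement in Section 6.3 and every entry of Table 6-2 rest on 28%. The Revision B to C summary in Section 4.1 records the performance goal rising from 23% to 28%. On this view Section 8.1.1 is a line missed during an amendment, and a later claim that 23% was meant would be hard to defend. Most of this stands: it is a consistency error, and the evidence on which value the design uses points one way. It does not remove the need to correct it, because Section 8.1.1 is operative text and no section is given precedence. Nor is 23% self-evidently a slip to a reader who sees the same figure as the lower end of the adjusted historical interval in Section 6.2.

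Some stronger readings should not be drawn:

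- A reader might infer that the rule should be fixed as a count, at least 40 of 107. But 107 is a planning number and Section 6.5 analyses observed data. At 119 observed, 44 successes are needed, and 40 of 119 has a lower limit of 25.2%, which fails.
- A reader might infer that Section 6.2 also sets 28% as the test value. It reports 28% as an adjusted estimate, but its hypothesis carries a symbol.
- A reader might infer that the endpoint has two time windows, because Section 12.6.5 heads the 12-month visit with ±60 days. The endpoint definition, both schedules and the core lab section all use ±8 weeks (56 days). The heading describes a visit, and differs by four days at each edge.
- A reader might want a joint efficacy-and-safety success rule added. Nothing in this contradiction bears on that.

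**Conclusion.** The contradiction is real and needs correcting before results are known. Section 8.1.1 carries a 23% pass mark, while Section 6.3, the sample size and the stated error rate hold only with 28%. At 107 evaluable subjects and with the exact interval, six outcomes (34 to 39 successes) would be judged differently by the two sections. The 23% rule would pass about ten times as often as the 28% rule when the true rate is 28% (0.221 / 0.022). At the sponsor's expected 41%, the two rules would still disagree 17.6% of the time.

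These sizes assume 107 observed subjects and the exact method named in Section 6.2. They illustrate the problem and are not fixed cut-offs.

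A reader might go further and conclude that the trial has no identifiable threshold, or that the sponsor left the choice open. The documents do not support that: the design figures identify 28%, and Section 8.1.1 is the outlier.

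**What to change.** In Section 8.1.1, replace the efficacy criterion with: the lower bound of the exact two-sided 95% confidence interval is greater than 28%. This matches Section 6.3 and Table 6-2. Keep it as a confidence-limit rule so that it applies to whatever number of subjects is observed; any success count should be given only as an example for a stated n.

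The cost is one line of protocol text. Sample size, visits and data collection do not change.

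As a separate minor item, reconcile the ±60 days heading the 12-month visit in Section 12.6.5 with the ±8 weeks in the endpoint definition and the schedules.
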